## 6. Statistical Analysis

### 6.1 Analysis Populations

The population of “all screened subjects” comprises subjects who signed the informed consent (ICF).

#### 6.1.1 Safety Population

The safety population comprises randomized subjects who have received at least 1 dose of the study drug.

#### 6.1.2 Intent-to-Treat Population

The intent-to-treat (ITT) population is defined as subjects who were randomized to treatment.

#### 6.1.3 Modified Intent-to-Treat Population

The modified intent-to-treat (MITT) population is defined as subjects who were randomized and received at least 1 dose of the study drug.

#### 6.1.4 Per Protocol Analysis Population

The per protocol (PP) population will include the Evaluable population (see Section 6.1.5) who have received at least 1 dose of study drug and did not have major protocol violations potentially interfering with the efficacy assessment. The PP exclusion criteria will be specified prior to the database lock and unblinding.

#### 6.1.5 Primary Analysis Population

The primary efficacy analysis population is the Evaluable Population defined as all randomized subjects who have received at least 1 infusion of study drug, and at study entry do not exhibit any of the following criteria:

1.  $>6$  eosinophils per hpf in at least one esophageal biopsy at baseline
2. Documented history of irritable bowel syndrome and baseline diarrhea intensity  $\geq 3$ .

- The complement to the Evaluable population will be referred to as the Excluded population. It is worth remarking that for this study, if a subject has a history of concomitant EoE, or if

esophagus looks suspicious for EoE or other condition, or if patient is symptomatic on screening dysphagia question, quantified by a score of  $>3$  on the dysphagia question on at least 1 day during screening, then the following is undertaken:

- A set of 2 fragments is collected from the distal esophagus
- A set of 2 fragments is collected from the mid-proximal esophagus
- Up to 2 extra specimens may be collected if there are any additional areas of interest.
- A count of  $>6$  eosinophils per hpf in at least one esophageal site will be considered diagnostic of at least having esophageal eosinophilia for the purposes of the study and in cases where there is a history of EoE this could reflect active eosinophilic esophagitis although fulfillment of the diagnostic criteria for that condition may not be certain (see Appendix 5 for details).

Analysis will be conducted on the complement population, referred to as Excluded Population, and is planned as exploratory. In addition, for completeness purposes, analysis will be conducted on the mITT population to show what the study results would have been on all the subjects prior to removing those with confounding conditions outlined above.

## 6.2 Disposition of Subjects

Subject demographics and reasons for screening failure will be summarized for screen-failed subjects. Subjects (n and %) who completed or discontinued from the study will be tabulated by treatment group and for both treatment groups combined. The primary reasons for study discontinuation will be included in the tabulation. The primary reasons may include, but are not limited to, any of the following:

- Subject withdrew consent
- Lost to follow-up
- Administrative reason
- Adverse event
- Investigator decision
- Failure to follow required study procedures
- Other

Subject disposition will be summarized for all enrolled subjects. Subject counts for the Safety, mITT, and PP populations will be included in the table. A data listing for subject disposition will be presented for all enrolled subjects.

### **6.3 Protocol Deviations**

Protocol deviations will include, but are not limited to

- Non-compliance with scheduled study visit
- Non-compliance with study treatment
- Received prohibited medications (see Protocol Section 8.1)
- Non-compliance with study inclusion or exclusion criteria
- Non-compliance with study assessment procedures

Subjects with major protocol deviations will be listed. The listing will include a brief description of the deviation, deviation category, and if applicable, study day when deviation occurred along with other pertinent information. If warranted by the sample size, subjects (n and %) with major protocol deviations will be tabulated by treatment group and by deviation category.

Subjects who are excluded from the PP population will be listed with reasons for exclusion.

### **6.4 Demographics and Baseline Subject Characteristics**

Descriptive statistics for subject characteristics and baseline values will be presented for all populations by treatment group and both treatment groups combined. Continuous variables will be summarized with n, mean, SD, and median. Categorical variables will be summarized with n and % of subjects for each category for the Evaluable, Excluded, mITT, and PP populations.

### **6.5 Baseline Disease Characteristics**

Baseline disease characteristics including demographics, weight, blood eosinophils ( $\geq 500$  cells/ $\mu$ L), IgE, IgE category ( $<45/\geq 45$ ), history of atopic dermatitis, functional GI symptoms, history of EG and/or EoD, duodenal eosinophils (per 3hpf in EoD), TSS total score at baseline, PRO symptom scores, and baseline elevated esophageal eosinophils histologic criteria will be included in the subject data listing.

### **6.6 Medical History**

Subject incidence (n and %) of medical history (and current medical condition before signing the informed consent) will be tabulated by the Medical Dictionary for Regulatory Activities (MedDRA), version 21.0) System Organ Class (SOC) and Preferred Term (PT).

### **6.7 Electrocardiogram**

A listing of electrocardiograms (ECG) overall interpretation at screening visit will be provided.

## **6.8 Pregnancy Test**

A listing of pregnancy test results will be provided.

## **6.9 Baseline Diet**

A listing of baseline and on-study diet assessment and compliance will be provided.

## **6.10 Treatments**

### **6.10.1 Treatment Compliance and Extent of Exposure**

Summaries of treatment compliance and exposure to AK002 will be based on the safety population.

Duration of treatment exposure is defined as the total number of days a subject is exposed to the study treatment. This will be calculated for each subject by taking the difference between the date of last dose minus the date of first dose, plus 1 (date of last dose – date of first dose +1). Duration of exposure will be summarized using descriptive statistics (n, mean, standard deviation, median, minimum, and maximum).

Treatment compliance is defined as the number of infusions that subjects received divided by 6 (i.e., total number of infusions expected)  $\times 100\%$ . Treatment compliance will be summarized descriptively. In addition, an overall compliance that includes adherence to treatment administration schedule and any interruptions will be included in the data listing.

The treatment infusion information (length, volume, rate, and interruption) will be included in the subject data listing.

### **6.10.2 Prior, Concomitant, and Newly Initiated Medications**

Prior medications and concomitant medications will be extracted from the Prior/Concomitant Medication CRF. Medications taken prior to Study Day 1 will be considered as prior medications; medications taken on or after Study Day 1 will be considered as concomitant medications; and newly initiated medication refers to any medication with a start date  $\geq$  Study Day 1. We note that a Prior Medication may also be a Concomitant Medication if the start date is prior to Study Day 1 and the end date is on/after Study Day 1. Medications will be coded using the WHO Drug Dictionary (WHODD March 2018 release) for PT and Anatomical Therapeutic Chemical (ATC) classification.

Medications will be tabulated separately based on the Safety population. The number (n and %) of subjects taking at least 1 medication and the number (%) of subjects taking each medication at

the preferred term level will be tabulated by ATC4, and PT. Subjects taking the same PT medication twice will only be counted once.

A subject data listing will be provided to include the reported medication name, the WHODD PT, ATC4, study day and pertinent subject information. A separate data listing will include subjects who have received prohibited medications.

## 6.11 Analysis of Primary Efficacy Endpoints

To assist the data interpretation, all ICE will be listed with pertinent subject information (subject ID, date of last infusion, ICE start/stop day, nature of ICE (reason for treatment/study discontinuation if applicable, description of AE, description of prohibited/restricted medication), baseline tissue eosinophil count and TSS, and most recent tissue eosinophil count and 2-week average of TSS). A summary table will be created to present number of subjects (n, %) by treatment group:

- Subjects with any ICE
  - Subjects by ICE category

### 6.11.1 Analysis of the First Co-Primary Endpoint

The first co-primary endpoint will be analyzed using the imputed data set (Section 5.4.1). Fisher's exact test (primary analysis) will be conducted comparing AK002 with placebo for the proportion of tissue eosinophil responders. Proportion of responders and the associated 95% confidence interval will be presented for each treatment group. The between group difference and the associated 95% confidence interval will also be computed and presented. A sample SAS code is as follows.

```
* COMPUTE 95% EXACT CONFIDENCE INTERVAL FOR %RESPONSE FOR INDIVIDUAL
TREATMENT ;
ods output BinomialCLs=CL ;
proc freq data=ADEF ;
  table RESP / out=CNTS bin(cl=midp) ;
  by TRTAN ;
run;

* COMPUTE 95% EXACT CONFIDENCE INTERVAL AND FISHERS EXACT P-VALUE FOR
BETWEEN TREATMENT DIFFERENCE ;
ods output FishersExact=PVAL(where=(name1='XP2_FISH'))
RiskDiffCol2=DIFF(where=(row='Difference')) ;
proc freq data=ADEF ;
  table TRTPN*RESP / riskdiff(cl=exact) exact ;
run ;
```

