The pattern-mixture model will be implemented using multiple imputations, and the inference of this sensitivity analysis will be based on the combined estimates using the standard multiple imputation technique. The imputed data sets will be analyzed with the same MMRM model utilized in the primary analysis and then summarized using PROC MIANALZE. The other is to analyze the average of Week 23 through Week 24 using ANCOVA with treatment and study site (with pooling by geographic location) as factors, gender and baseline TSS (continuous) as covariates. Missing Week 23 through Week 24 weekly TSS will be imputed prior to ANCOVA using SAS PROC MI under the MAR assumption. Detailed specifications for the missing data imputation will be provided in the SAP.

Analysis of binary secondary endpoints will be based on the CMH test stratified by the randomization stratification factor (baseline TSS <28 vs \geq 28).

Change from baseline in continuous secondary outcomes measured at multiple post-baseline time points will be analyzed longitudinally using MMRM techniques. The model will include fixed effects for baseline value, treatment, week, treatment by week interaction, baseline value by week interaction, and allow for random subject effects. The model variance-covariance matrix will be unstructured. However, if computation does not converge, the matrix will take the form of Toeplitz, AR(1), and compound symmetry, whichever converges first. The Kenward-Rogers approach for computing denominator degrees of freedom will be used to account appropriately for pooling of within-subject and between-subject variance estimates. Least square means and the 95% CI for the between group difference will be estimated for each week.

To control for the overall false-positive error rate, the hypothesis testing for the primary and secondary endpoints using the Evaluable population in the subgroup defined above as the only population for primary inference are ordered as follows:

- The 2 co-primary efficacy endpoints will each be tested 2-sided at $\alpha=0.05$ level. If both tests are statistically significant, the hypothesis tests for the secondary endpoints will proceed sequentially based on the order specified in Section 4.2.

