In the randomized, double-blind, placebo-controlled, Phase 2 study of AK002 in 65 patients with EG and/or EoD, patients were randomized to receive monthly doses of placebo, low dose AK002 (0.3, 1, 1, and 1 mg/kg), or high dose AK002 (0.3, 1, 3, and 3 mg/kg) in a 1:1:1 ratio. All primary and secondary endpoints were met in the study. There was a 97% and 92% mean reduction in eosinophils in the stomach/duodenum for the high dose and low dose AK002-treated patients, respectively, vs a 10% increase for placebo-treated patients ($p<0.0001$). There was also a statistically significant reduction in total symptom score (TSS) of 58% in the high dose AK002 group and 49% reduction in the low dose group AK002 vs a 24% reduction in the placebo group ($p=0.0012$ and $p=0.015$, respectively). Improvement in symptoms were observed within 24 hours of the first dose of study drug. In addition, 70% of high dose treated patients and 68% of low dose treated patients were treatment responders (defined as $>30\%$ improvement in TSS and $>75\%$ reduction from baseline in tissue eosinophils) vs 5% of placebo-treated patients ($p<0.0001$) ([Dellon, 2020](#)).

Among the 65 patients, there were patients with EG without EoD, patients with EoD without EG, and patients with both EG and EoD, and these subgroups had similar symptoms and symptom severity. The treatment benefit of AK002 was observed across all of the subgroups, whether eosinophilia was reported in the duodenum with or without concomitant EG.

Patients with EoD without EG had a similar histologic response on AK002 treatment as those with EG with or without EoD (All EG). AK002 resulted in a -99.5% and -91.5% mean change in tissue eosinophils in patients with EoD without EG and in patients with EG ± EoD, respectively. The proportion of patients achieving ≤ 1 eosinophil/hpf at the end of treatment was also similar (93.3% and 75% of EoD without EG and All EG, respectively), compared to no patients on placebo. Additionally, symptomatic improvement was similar; EoD without EG patients had a mean change in TSS of -57.4%, and all EG patients experienced a -51% mean change in TSS.

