### 3.5 Determination of Sample Size

A total of approximately 80 subjects will be enrolled.

**First Co-Primary Endpoint:** A sample size of 40 subjects per treatment group will have >90% power to demonstrate a greater proportion of histologic responders at Week 24 in AK002 subjects compared to placebo subjects, assuming the proportions of histologic responders are 0.6 and 0.1 in AK002 and placebo groups, respectively.

**Second Co-Primary Endpoint:** A sample size of approximately 40 patients per treatment group will provide 80% power to detect a statistically significant difference of 7.4 points between AK002 and placebo in the mean reduction from Baseline in TSS at Weeks 23-24, assuming a common standard deviation of 12.5 points (AK002-003 data on file).

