#### **4.2.6 Summary Measure of the Estimand**

- Percent (and 95% CI) of subjects having tissue eosinophil response at Week 24 in the AK002 and Placebo treatment groups and the absolute difference (and 95% CI) in the percent response between treatments.
- Least squares mean (LSM) (and standard error [SE]) of change from baseline to the average of Weeks 23–24 TSS and the between treatment difference in the AK002 and placebo treatment groups LSM. LSM and SE derived from mixed model repeated measures (MMRM) model.

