## 6.11.2 Sensitivity Analysis of the First Co-Primary Endpoint

Sensitivity analysis may be carried out using the Cochran-Mantel-Haenszel (CMH) test stratified by the randomization stratification factor (baseline TSS [ $<28$  vs.  $\geq 28$ ]) to assess robustness of the Fisher's exact test results.

A sample SAS code for the pairwise comparison is as follows.

```
* COMPUTES CMH P-VALUE AND NEWCOMBE COMMON RISK DIFFERENCE ;
ods output CMH=PVAL(where=(alhypothesis='Row Mean Scores Differ')) ;
CommonPdiff=DIFF;
proc freq data=ADEF ;
  tables TSS_STRAT*TRTP*RESP / cmh commonriskdiff
  (cl=NEWCOMBE) ;
run ;
```

The rationale for specifying the Fisher's exact test as the primary analysis as opposed to specifying the CMH is because when a stratum has 100% response for 1 treatment group and 0% response for another treatment group, the CMH test may lose efficiency or not be computable. This is evident from the Phase 2 study outcome.

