### 6.12.2 Proportion of Subjects Achieving Peak Duodenal Intraepithelial Eosinophil Count of $\leq 1$ Cell/hpf

This endpoint will be analyzed using the Fisher's exact test similar to the analysis for the first co-primary endpoint (Section 6.11.1).

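### The sample code for the responder-difference interval is labelled exact but its request is incomplete; run as written it would give Wald limits, which matters mainly for the ≤1 cell/hpf secondary

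*SAP*

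**What the plan says.** SAP 4.2.6 makes the "absolute difference (and 95% CI) in the percent response between treatments" part of the summary measure for the histology co-primary. SAP 6.11.1 names Fisher's exact test as the primary analysis and promises a 95% interval for the between-group difference. Neither its prose nor Protocol 15.6.1 says which interval.

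The sample code in 6.11.1 is therefore the only specification. The comment above the relevant step begins "COMPUTE 95% EXACT CONFIDENCE INTERVAL AND FISHERS EXACT P-VALUE FOR" and goes on to name the between-treatment difference. The step is "table TRTPN*RESP / riskdiff(cl=exact) exact". No separate EXACT statement follows, and the ODS line keeps the Difference row of `RiskDiffCol2`.

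Two secondaries point back to this section. For the ≤1 cell/hpf endpoint, SAP 6.12.2 says: "This endpoint will be analyzed using the Fisher's exact test similar to the analysis for the first co-primary endpoint". SAP 6.12.3 does the same for treatment responders. SAP 6.11.2 prefers Fisher's test to CMH because CMH may fail "when a stratum has 100% response for 1 treatment group and 0% response for another treatment group", and cites Phase 2 as evidence.

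**The concern.** In PROC FREQ, exact unconditional limits for a risk difference are computed when a separate EXACT statement names RISKDIFF. The `cl=exact` suboption asks for those limits to be displayed, and the trailing `exact` on the TABLE statement asks for Fisher's test. Without the EXACT statement, the retained row carries the default Wald limits.

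The Wald interval is poor when one proportion is near 1 and the other near 0. It can run past 100%, and it has zero width when every AK002 patient and no placebo patient responds. Printed under an exact label beside an exact p-value, it would overstate the precision of an estimate that the SAP treats as a summary measure. Rates of that kind have been seen for one of the endpoints that use this code.

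**Working it through.** **Inputs.**
- 40 per arm and 60% vs 10%: SAP 3.5.
- 84.6% vs 4.5%: AK002-016 histology, Protocol 2.3, Table 1.
- ≤1 eosinophil/hpf on AK002 in Phase 2, "93.3% and 75% of EoD without EG and All EG, respectively", with no placebo patient reaching it: Protocol 2.3. I use 93.3% vs 0%, because this trial enrols EoD without EG.
- Phase 2 treatment responders, 70% and 68% vs 5%: Protocol 2.3.
- Assumption: 30 to 40 Evaluable patients per arm. About 80 are randomized, and the Evaluable population is a subset of unstated size.

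**The plan's own figure.** SAP 3.5 says "A sample size of 40 subjects per treatment group will have >90% power to demonstrate" the difference. With a mean proportion of 0.35, the pooled z calculation is (0.5√40 − 1.96√(2 × 0.35 × 0.65)) / √(0.6 × 0.4 + 0.1 × 0.9) = (3.162 − 1.322) / 0.574 = 3.20, or 99.9% power. Full enumeration of Fisher's test gives 99.8%. The stated figure holds, and the interval does not enter it.

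**Intervals at example counts.** The Wald interval is d ± 1.96√(p₁(1−p₁)/n + p₂(1−p₂)/n). For 37/40 vs 0/40, d = 0.925 and SE = √(0.925 × 0.075/40) = 0.0416. The limits are 0.925 ± 0.082, or 84.3% to 100.7%. The counts below are illustrations at 40 per arm. The exact limits invert two one-sided 2.5% tests on the raw difference.

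| Responders | Wald | Exact unconditional | Newcombe |
|---|---|---|---|
| 24 vs 4 | 32.2 to 67.8 | 28.1 to 68.0 | 29.8 to 64.9 |
| 34 vs 2 | 67.0 to 93.0 | 62.5 to 91.2 | 61.8 to 88.7 |
| 37 vs 0 | 84.3 to 100.7 | 78.9 to 98.4 | 77.3 to 97.4 |
| 40 vs 0 | 100 to 100 | 91.0 to 100 | 87.6 to 100 |

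A score-based exact interval is close to the raw-difference one: 79.6 to 98.4 for 37 vs 0, and 91.0 to 100 for 40 vs 0.

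**Wald behaviour over repeated trials.** I enumerated both binomials in full at 30, 35 and 40 per arm.

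| True rates | Coverage | Upper limit >100% | Zero width |
|---|---|---|---|
| 60% vs 10% | 94.3, 94.4, 94.4% | none | none |
| 84.6% vs 4.5% | 93.7, 91.9, 90.3% | 13, 7, 3% | at most 0.2% |
| 70% vs 5% | 91.9, 93.2, 94.3% | below 0.3% | none |
| 93.3% vs 0% | 87.2, 90.4, 93.3% | 74, 71, 66% | 12.5, 8.8, 6.2% |

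At 68% vs 5%, coverage is 93.5–93.7%.

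The last row can be checked by hand. With no placebo responders, the width is zero only if all AK002 patients respond, so the probability is 0.933ⁿ: 12.5% at n = 30 and 6.2% at n = 40. With k AK002 non-responders, the upper limit passes 100% when 1 ≤ k < 3.84/(1 + 3.84/n). That means k = 1, 2 or 3 at all three sizes. The zero-width cases account for nearly all the missed coverage (6.2 of 6.7 points at n = 40).

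Newcombe coverage at 93.3% vs 0% is 95.3% at 30 per arm and 95.1% at 40.

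**Sensitivity to the placebo rate.** Lower Wald coverage needs a placebo rate that the documents do not give: 81.8% at an assumed 1% with 40 per arm, and 81.2% at an assumed 2% with 35 per arm.

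**The case against.** Four points on the other side carry weight.

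- **The code does ask for exact limits.** A reader might infer that it never does, but `cl=exact` is in the line. The request is incomplete, and the retained output table does not match it.
- **A Wald interval in the final report is not certain.** The code is introduced as a sample, its comment states exact intent, and a programmer may notice. That step also rests on software behaviour that the documents do not describe; the code was not run in SAS. Still, no other text defines the interval. The independent reprogramming in SAP section 7 checks that two programs agree, and two programmers who follow the same sample could agree on the same wrong limits.
- **The failure is not general.** One might infer that the interval breaks down for the co-primary and both secondaries alike. The figures do not support that: Wald is adequate at the planning rates and tolerable at the treatment-responder rates. The stratum remark in SAP 6.11.2 explains the choice of test and does not forecast whole-arm rates. Counting intercurrent events as non-response also pulls the active rate down. AK002-016 is an imperfect guide, because its endpoint used peak gastric and/or duodenal counts in EG/EoD.
- **No decision turns on it.** Success and the testing sequence use p-values, and in every example the lower limit is far above zero by any method.

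**Conclusion.** The point holds as an estimation and reporting defect in SAP 6.11.1, inherited by 6.12.2 and 6.12.3. The interval is labelled exact, its method is not named in the text, and the sample code run as written would yield Wald limits.

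The material damage is to the ≤1 cell/hpf secondary if the Phase 2 rates recur. For the co-primary, the loss is negligible at the planning rates and moderate at the AK002-016 rates.

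This conclusion assumes 30 to 40 Evaluable patients per arm, the earlier studies' rates as guides, and the PROC FREQ behaviour described above, which a short test run would confirm. Even if the software behaved otherwise, the method for a co-primary summary measure would still need naming. A reader might go further and infer a threat to the co-primary's type I error or power. The documents give no basis for that, because neither depends on the interval.

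**What to change.** In SAP 6.11.1, name the interval method in the text and make the code deliver it. Either option works:

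1. Keep an exact interval. Add an EXACT statement naming RISKDIFF (with the score method if preferred), and report the exact limits for the difference.
2. Use Newcombe, already the choice in SAP 6.11.2, or Miettinen–Nurminen. Read the matching confidence-limit table, and drop the word exact for the difference.

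State that the same interval applies in 6.12.2 and 6.12.3, and test-run the code on 40/40 vs 0/40 before unblinding. The cost is about one line of code and one phrase. Reported intervals will usually be somewhat wider: at 37/40 vs 0/40 the width goes from 16.4 points (Wald) to 19.5 (exact) or 20.1 (Newcombe). No test or sample size changes.
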